## 7. PLANNED ANALYSIS

Safety analysis (refer to [Section 7.8](#)) will be performed by [REDACTED] and will be presented in Sections 15.1 to 15.4 of the CTR and in Appendix 16.2 and 16.1.13.1.

Inferential statistical analyses of PK endpoints (refer to [Section 7.4](#)) will also be performed by [REDACTED] and will be presented in Section 15.5 of the CTR and in Appendix 16.1.13.3.

Descriptive data analysis of PK endpoints and concentrations will be performed by the department of [REDACTED] at [REDACTED] and will be presented in Section 15.6 of the CTR and in Appendix 16.1.13.5.

The format of the listings and tables will follow the BI standards (see “Standards for Reporting of Clinical Trials and Project Summaries” ([8](#))) with the exception of those generated for PK-calculations following BI standards for PK/PD analysis ([9](#)).

The individual values of all subjects will be listed, sorted by treatment sequence, subject number and visit and time point. The listings will be included in Appendix 16.2 of the CTR.

The following standard descriptive statistical parameters will be displayed in summary tables of continuous variables:

N	number non-missing observations
Mean	arithmetic mean
SD	standard deviation
Min	minimum
Median	median
Max	maximum

For analyte concentrations and PK parameters, the following descriptive statistics will additionally be calculated (if needed):

Nobs	number of observations
CV	arithmetic coefficient of variation
gMean	geometric mean
gCV	geometric coefficient of variation
P10	10 th percentile
Q1	1 st quartile
Q3	3 rd quartile
P90	90 th percentile

The data format for descriptive statistics of concentrations will be identical to the data format of the respective concentrations. The descriptive statistics of PK parameters will be calculated using the individual values with the number of decimal places as provided by the evaluation program. Then the individual values as well as the descriptive statistics will be reported with three significant digits in the CTR.

Tabulations of frequencies for categorical data will include all possible categories available in the CRF and will display the number of observations in a category, as well as the percentage (%). Percentages will be given in integer numbers due to the small sample size of <100. Percentages will be based on all subjects in the respective subject set whether they have non-missing values or not. The category 'missing' will be displayed only if there are actually missing values.

Units of variables should be given in the titles or column/row descriptors in brackets (e.g. (mg)).

#### Exclusion of PK parameters

The ADS “ADPP” (PK parameters) contains column variables APEX and APEXCO indicating inclusion/exclusion (APEX) of a PK parameter and an analysis flag comment (APEXCO). All analyses based on the PKS will include parameters only if they are not flagged for exclusion, that is APEX is equal to “Included”.

#### Exclusion of PK concentrations

The ADS “ADPC” (PK concentrations per time-point or per time-interval) contains column variables ACEX and ACEXCO indicating inclusion/exclusion (ACEX) of a concentration and an analysis flag comment (ACEXCO). Exclusion of a concentration depends on the analysis flag comment ACEXCO. For example, if ACEXCO is set to

- ‘ALL CALC’, the value will be excluded for all types of analyses based on concentrations.
- ‘DESC STATS’ the value will be excluded from descriptive evaluations per planned time point/time interval.
- ‘HALF LIFE’, the value will be excluded from half-life calculation (and, as a consequence, any calculation that relies on  $\lambda_z$ ) only; the value is included for all other analyses.

If ACEXCO contains the addition ‘TIME VIOLATION’ or ‘TIME DEVIATION’ the value can be used for further analyses based on actual times. Excluded concentration itself will be listed in the CTR associated with an appropriate flag.

Further details are given in “Noncompartmental Pharmacokinetic / Pharmacodynamic Analyses of Clinical Studies” ([7](#)) and “Description of Analytical Transfer Files and PK/PD Data Files” ([10](#)).

## 7.1 DEMOGRAPHIC AND OTHER BASELINE CHARACTERISTICS

Only descriptive statistics are planned for this section of the CTR, based on the TS.  
The data will be summarised by the overall treatment sequence.

## 7.2 CONCOMITANT DISEASES AND MEDICATION

Only descriptive statistics are planned for this section of the CTR, based on the TS.

Concomitant diseases and non-drug therapies will be coded according to the version defined in the decision log (4) of the coding system of the Medical Dictionary for Drug Regulatory Activities (MedDRA). Concomitant medications will be coded according to the most recent version of the World Health Organization Drug Dictionary (WHO-DD). The coding version number will be displayed as a footnote in the respective output.

In the remaining document ‘therapy’ will be used for non-drug therapies and concomitant medications

### Section 7.2.5 of the CTP:

*Previous and concomitant therapies will be presented for the overall treatment sequence (‘BI / ITZ+BI’) without consideration of time intervals and treatment periods.*

A therapy will be considered concomitant to a treatment, if it

- is ongoing at the time of study drug administration, or
- starts within the analysis phase of the respective treatment (see [Section 6.1](#) for a definition of treatments and analysis phases).

The diagnoses and therapies will be listed. Subjects without any concomitant diagnoses or concomitant therapies will be marked with a “No” in the respective column.

The relevance of the concomitant therapies to the evaluation of PK data will be decided no later than at the RPM.

### 7.3 TREATMENT COMPLIANCE

Treatment compliance will not be analysed as a specific endpoint, but judged by observed analyte concentrations, cf. **Section 4.3 of the CTP**:

*Compliance will be assured by administration of all trial medication in the trial centre under supervision of the investigating physician or a designee. The measured plasma concentrations of trial medication will provide additional confirmation of compliance.*

Treatment exposure to BI 1584862 is defined as the number of doses and total dose of BI 1584862 per subject.

Treatment exposure to itraconazole is defined as the number of doses and total dose of itraconazole per subject.

Any deviations from complete [REDACTED] will be addressed in the RPM and described in the CTR.

## 7.4 PRIMARY OBJECTIVE ANALYSIS

### 7.4.1 Main analysis

#### Section 7.2.2 of the CTP:

*The statistical model used for the analysis of the primary and secondary endpoints (refer to [Section 5.1](#) and [Section 5.2.2](#)) will be an analysis of variance (ANOVA) model on the logarithmic scale. That is, the PK endpoints will be log-transformed (natural logarithm) prior to fitting the ANOVA model. This model will include effects accounting for the following sources of variation: subjects and treatment. The effect 'subjects' will be considered as random, whereas 'treatment' will be considered as fixed. The model is described by the following equation:*

$$y_{km} = \mu + s_m + \tau_k + e_{km}, \text{ where}$$

$y_{km}$  = logarithm of response measured on subject  $m$  receiving treatment  $k$ ,

$\mu$  = the overall mean,

$s_m$  = the effect associated with the  $m^{\text{th}}$  subject,  $m = 1, 2, \dots, n$

$\tau_k$  = the  $k^{\text{th}}$  treatment effect,  $k = 1, 2$ ,

$e_{km}$  = the random error associated with the  $m^{\text{th}}$  subject who received treatment  $k$ .

where  $s_m \sim N(0, \sigma_B^2)$  i.i.d.,  $e_{km} \sim N(0, \sigma_W^2)$  i.i.d. and  $s_m, e_{km}$  are independent random variables and  $n$  is the total number of subjects included in the trial.

Point estimates for the ratios of the geometric means (test/reference) for the primary endpoints [...] and their two-sided 90% confidence intervals (CIs) will be provided.

For each primary endpoint, the difference between the expected mean for log response of the test treatment – log response of the reference treatment will be estimated by the difference in the corresponding adjusted means (Least Squares Means). Additionally their two-sided 90% confidence intervals will be calculated based on the residual error from the ANOVA and quantiles from the  $t$  distribution. These quantities will then be back-transformed to the original scale to provide the point estimate and 90% CIs for each endpoint.

The implementation for this analysis will be accomplished by using the CSD macros based on the PKS. The following SAS code can be used:

```
PROC MIXED DATA=indata METHOD=REML;
  CLASS subject treatment;
  MODEL logpk = treatment / DDFM=KR;
  RANDOM subject;
  LSMEANS treatment / PDIF CL ALPHA=0.1;
  ESTIMATE 'T-R' treatment 1 -1;
RUN;
```

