7.2.2 Primary endpoint analyses

Primary analyses

The statistical model used for the analysis of the primary endpoints will be an analysis of variance (ANOVA) model on the logarithmic scale. That is, the PK endpoints will be log-transformed (natural logarithm) prior to fitting the ANOVA model. This model will include effects accounting for the following sources of variation: subjects and treatment. The effect 'subjects' will be considered as random, whereas 'treatment' will be considered as fixed. The model is described by the following equation:

$$y_{km} = \mu + s_m + \tau_k + e_{km}, \text{ where}$$

y_{km} = logarithm of response measured on subject m in receiving treatment k ,

μ = the overall mean

s_m = the effect associated with the m^{th} subject, $m = 1, 2, \dots, n$

τ_k = the k^{th} treatment effect, $k = 1, 2$

e_{km} = the random error associated with the m^{th} subject who received treatment k

where $s_m \sim N(0, \sigma_B^2)$ i.i.d., $e_{km} \sim N(0, \sigma_W^2)$ i.i.d. and s_m, e_{km} are independent random variables and n is the total number of subjects included in the trial.

Point estimates for the ratios of the geometric means (test/reference) for the primary endpoints (see Section [2.1](#)) and their two-sided 90% confidence intervals (CIs) will be provided.

For each primary endpoint, the difference between the expected mean for log response of the test treatment – log response of the reference treatment will be estimated by the difference in the corresponding adjusted means (Least Squares Means). Additionally their two-sided 90% confidence intervals will be calculated based on the residual error from the ANOVA and quantiles from the t-distribution. These quantities will then be back-transformed to the original scale to provide the point estimate and 90% CIs for each endpoint.

Further exploratory analyses

The same statistical model as stated above will be repeated for the primary endpoints but with all sources of variation (, ‘subjects’, ‘treatment’) considered as fixed effects.

In addition to the model based approach the primary endpoints will be analysed descriptively.

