## 6. GENERAL ANALYSIS DEFINITIONS

### 6.1 TREATMENTS

For basic study information on treatments to be administered and selection of doses, refer to CTP Sections 3 and 4.

This trial is designed as an open-label, two-treatment, two-period, fixed sequence design trial in 14 healthy male subjects with a wash-out phase of [REDACTED] between the single dose administrations of BI 1584862 in the two periods.

For details of dosage and formulation see Table 6.1:1 below.

Table 6.1: 1 Treatments and labels used in the analysis

Treatment	Short label
R BI 1584862, [REDACTED]	BI
T Itraconazole oral solution, 200 mg, qd + BI 1584862, [REDACTED]	ITZ+BI

The sequence for “R-T” is named “BI / ITZ+BI” accordingly.

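### Under SAS default ordering and the SAP's own treatment labels, the sample code for the primary analysis gives reference minus test, not the specified test minus reference

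*SAP*

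**What the plan says.** The text gives the direction clearly. Protocol section 7.2.2 calls for "Point estimates for the ratios of the geometric means (test/reference) for the primary endpoints" with two-sided 90% CIs. SAP section 7.4.1 repeats this and adds that, on the log scale, "the difference between the expected mean for log response of the test treatment – log response of the reference treatment will be estimated" before back-transformation.

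The SAP then says that the company's CSD macros will carry out the analysis, and offers SAS code that may be used. Four of its statements matter here:

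- "PROC MIXED DATA=indata METHOD=REML"
- "CLASS subject treatment"
- "LSMEANS treatment / PDIF CL ALPHA=0.1"
- "ESTIMATE 'T-R' treatment 1 -1"

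No ORDER= option appears. LSMEANS names no reference level. The ESTIMATE line requests no confidence limits.

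The treatment names are in SAP section 6.1, in the table headed "Table 6.1: 1 Treatments and labels used in the analysis": R has the short label BI, and T has the short label ITZ+BI. The text below the table adds: "The sequence for “R-T” is named “BI / ITZ+BI” accordingly". Neither document says how the variable `treatment` is coded or ordered in `indata`.

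**The concern.** ESTIMATE coefficients apply to class levels in sorted order. If the reference sorts first, a contrast labelled test minus reference holds the opposite difference. The confidence limits would not reveal this, because the LSMEANS difference takes the same direction and the two outputs would agree with each other.

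This is the only code the SAP gives for the main analysis. It serves both primary endpoints (AUC0-∞ and Cmax), and section 7.4.1 applies the same model to the secondary endpoint, AUC0-tz. Protocol section 1.3 says the trial looks for increases in BI 1584862 exposure that could affect patient safety. In an inverted ratio, an increase reads as a decrease.

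**Working it through.** **Inputs from the documents.** Required direction: T minus R, then T/R. Coefficients: +1 on the first level, -1 on the second. No ORDER= option. Labels: R/T and BI/ITZ+BI. Two-sided 90% confidence, which ALPHA=0.1 matches. N: 14 entered, at least 12 evaluable (protocol section 7.5). Illustrative ratios: 100, 200 and 300% (protocol Table 7.5: 1).

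**Inputs from outside the documents.** SAS sorts class levels by formatted value by default, and LSMEANS differences are formed as first level minus second. The intra-individual gCV is redacted, so 15 to 30% is assumed, for illustration only. The body of Table 7.5: 1 is also redacted, so the plan has no printed figure to reproduce.

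**Step 1: level order.** R sorts before T, and BI before ITZ+BI. The spelled-out pairs Reference/Test and BI 1584862/Itraconazole... also put the reference first.

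**Step 2: contrast.** With the reference first, (+1)·R + (-1)·T = R - T. Back-transformed, exp(R - T) = 1/(T/R):

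- T/R = 200% gives 1/2.00 = 50.0%
- T/R = 300% gives 1/3.00 = 33.3%
- T/R = 100% gives 100%, so the inversion is invisible where there is no effect

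**Step 3: confidence limits.** ESTIMATE requests none, so the 90% limits come from LSMEANS, also as R minus T. The log-scale half-width is w = t(0.95, N-1) · σ_W · √(2/N), with σ_W = √ln(1 + gCV²). For N = 12 and an assumed gCV of 20%:

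- σ_W = √ln(1.04) = 0.198
- w = 1.796 × 0.198 × 0.408 = 0.145, and exp(w) = 1.156

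| True T/R | Specified direction (90% CI) | Code under default order (90% CI) |
|---|---|---|
| 200% | 200% (173.0 to 231.3) | 50.0% (43.2 to 57.8) |
| 300% | 300% (259.5 to 346.9) | 33.3% (28.8 to 38.5) |

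For a true 200%, over N = 12 to 14 and gCV 15 to 30%, the inverted interval runs from 40.3 to 62.0 at its widest and 45.2 to 55.2 at its narrowest. The half-width w is the same in both directions.

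These are plain 90% CIs. Table 7.5: 1 concerns precision reached with 95% probability, which multiplies w by √(χ²(0.95, 11)/11) = 1.337. At the same inputs that gives 164.7 to 242.9% for a ratio of 200%. The choice does not affect the direction.

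**Step 4: model check.** A REML mixed model was fitted to one simulated data set (N = 14, true T/R = 2, log-scale SDs 0.4 between and 0.2 within subjects). Fitted means were -0.0070 for R and 0.7569 for T.

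- Coefficients 1 -1: -0.0070 - 0.7569 = -0.7639, and exp(-0.7639) = 0.466 (90% CI 0.399 to 0.543)
- Coefficients -1 1: 2.147 (90% CI 1.840 to 2.504)

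The intervals use the paired differences with 13 degrees of freedom. The two results are reciprocals.

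**The case against.** The strongest reply is that the specification is right and the code is only an aid. Protocol and SAP text both require test over reference. The CSD macros do the analysis, they are not in the documents, and nothing shows that they invert anything. The sample code uses generic names, does not back-transform, and would be correct if test were ordered first in the data. SAP section 6.1 refers detailed handling of treatments to a technical data set plan and a reviewer's guide, although that sentence follows the adverse-event displays and may not cover the PK data.

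Detection is also likely. LSMEANS gives each treatment's adjusted mean, and SAP section 7 places descriptive PK statistics, with geometric means if needed, in section 15.6 of the trial report. A doubling shown as a halving would conflict with both.

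Most of this stands. A reader might infer that the trial's reported ratios will be inverted and the interaction conclusion reversed. The documents do not support that. It would require this code, or a macro call in the same order, to be used as written, its output to be back-transformed, and the mismatch to go unnoticed.

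The reply does not remove the fault in the code. Every label pair printed for these treatments sorts the reference first, so the code contradicts its own label under the SAP's own names unless an unstated ordering applies. No check of direction between the inferential and descriptive results is written down.

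**Conclusion.** The point holds as a conditional fault in the sample code. Under SAS default ordering and the SAP's labels, both the ESTIMATE contrast and the LSMEANS difference are R minus T, against the label and against the specified ratio. If the code were followed and back-transformed, the error would be an exact reciprocal (200% to 50%, 300% to 33.3%) at any gCV, with no change in log-scale width, precision or confidence level.

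This rests on two things outside the documents: the SAS defaults, and the assumption that `treatment` carries one of the documented labels with no other ordering. It does not show that the macros, or the results to be reported, are inverted. It is still worth correcting, because this is the only code in a final SAP for both primary endpoints.

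**What to change.** In SAP section 7.4.1:

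1. State beside the code how `treatment` is coded and in what order its levels fall.
2. Name the reference level: `LSMEANS treatment / PDIFF=CONTROL('<reference level>') CL ALPHA=0.1;`. The difference is then test minus reference whatever the sort order.
3. Match the ESTIMATE coefficients to the stated order and request 90% limits. Where the reference sorts first: `ESTIMATE 'T-R' treatment -1 1 / CL ALPHA=0.1;`. Changing these coefficients alone is not enough. It would leave the LSMEANS limits as R minus T, and a hard-coded -1 1 would itself invert the contrast if test were ordered first.
4. Confirm that the CSD macro call uses the same direction.
5. Check that each back-transformed ratio points the same way as the descriptive geometric means.

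The cost is two lines of code, a sentence on coding and two checks. The SAP is final at version 1.0, so the change needs a new SAP version. The protocol text is already right and needs no amendment. No further data or subjects are needed.

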#### **7.4.4 Supplementary analysis**

No supplementary analysis is planned.

### **7.5 SECONDARY OBJECTIVE ANALYSIS**

#### **7.5.1 Key secondary objective analysis**

This section is not applicable as no key secondary objective has been specified in the protocol.

#### **7.5.2 Secondary objective analysis**

This section is not applicable as no key secondary objective has been specified in the protocol.

## 7.7 EXTENT OF EXPOSURE

Descriptive statistics of number of doses and calculated total doses of BI 1584862 and itraconazole are planned for this section of the CTR based on the TS. The date and time of drug administration will be listed for each subject.

## 7.8 SAFETY ANALYSIS

All safety analyses will be performed on the TS.

The safety data for treated subjects who failed to complete the study (dropouts or withdrawals) will be reported as far as their data are available.

**Section 7.2.5 of the CTP:** *For all analyses, the treatment actually administered (= treatment at onset) to the subject will be used (any deviations from the assigned treatment will be discussed in the minutes of the Report Planning Meeting).*

### 7.8.1 Adverse Events

AEs will be coded using MedDRA. The coding version number will be displayed as a footnote in the respective output.

Unless otherwise specified, the analyses of AEs will be descriptive in nature. All analyses of AEs will be based on the number of subjects with AEs and NOT on the number of AEs. BI standards as presented in “Analysis and Presentation of Adverse Event Data from Clinical Trials – Display Template” ([11](#)) and “Analysis and Presentation of AE data from clinical trials” ([12](#)) will be applied.

The analysis of AEs will be based on the concept of treatment emergent AEs. That means that all AEs will be assigned to ‘screening’, ‘on-treatment’ or ‘follow-up’ phases as defined in [Section 6.1](#). AEs will be analysed based on actual treatments, as defined in [Table 6.1: 1](#) and [Table 6.1: 2](#).

An overall summary of adverse events will be presented. This overall summary will comprise summary statistics for the class of AESIs.

#### Section 5.2.6.1.4 of the CTP:

*The following are considered as AESIs:*

- Potential severe DILI

*A potential severe Drug Induced Liver Injury (DILI) that requires follow-up is defined by the following alterations of hepatic laboratory parameters:*

- o An elevation of AST (aspartate aminotransferase) and/or ALT (alanine aminotransferase)  $\geq 3$ -fold ULN combined with an elevation of total bilirubin  $\geq 2$ -fold ULN measured in the same blood sample, or in samples drawn within 30 days of each other, or*
- o Aminotransferase (ALT, and/or AST) elevations  $\geq 10$ -fold ULN*

*These lab findings constitute a hepatic injury alert and the subjects showing these lab abnormalities need to be followed up according to the 'DILI checklist' provided in the ISF. In case of clinical symptoms of hepatic injury (icterus, unexplained encephalopathy, unexplained coagulopathy, right upper quadrant abdominal pain, etc.) without lab results (ALT, AST, total bilirubin) available, the Investigator should make sure that these parameters are analysed, if necessary in an unscheduled blood test.. Should the results meet the criteria of hepatic injury alert, the procedures described in the DILI checklist should be followed.*

The investigator had to classify on the eCRF whether an observed AE was an AESI or not.

According to ICH E3 ([13](#)), in addition to Deaths and serious adverse events, 'other significant' AEs need to be listed in the CTR. These will be any non-serious adverse event that led to an action taken with study drug (e.g. discontinuation or dose reduced or interrupted).

The frequency of subjects with AEs will be summarised by treatment, primary system organ class (SOC) and preferred term (PT). Separate tables will be provided for subjects with serious AEs, for subjects with investigator-defined drug-related AEs, for subjects with investigator-defined drug-related serious adverse events, for subjects with AESIs and for subjects with AEs leading to discontinuation. In addition, the frequency of subjects with AEs will be summarised by worst intensity, treatment, primary system organ class (SOC) and preferred term (PT).

The system organ classes will be sorted by default alphabetically, PTs will be sorted by descending frequency (within SOC).

In addition, for disclosure of AE data on ClinicalTrials.gov, frequencies of subjects with non-serious AEs that had an incidence of  $> 5\%$  (in preferred terms) for at least one treatment will be summarised by treatment, primary SOC and PT. The frequency of subjects with SAEs will also be summarised.

For disclosure of AE data in the EudraCT register, the frequency of AEs and the frequency of non-serious AEs with an incidence of greater than 5 % (in preferred terms) and the frequency of SAEs will be summarized.

